Interventions	
Participants that are SzNET positive will receive a loading ASM combination dose of Levetiracetam (60mg/kg) and Phenobarbital (20 mg/kg), followed by maintenance dosing for weight and age of both medications from three to ten days until the repeat rs-fMRI.
 
If care team considers either of those medications cannot be used, then they are allowed to administer any other combination of two ASM from the following list as the loading dose:
 
 1. Phenobarbital 20 mg/kg 2. Levetiracetam 60mg/kg 3. Lacosamide 10 mg/kg 4. Valproate 30 mg/kg 5. Fosphenytoin 20 mg/kg 
Maintenance dose: Standard dosing for weight and age of both medications used for the loading dose from three to ten days until the repeat rs-fMRI.
 
Participants with GCS 9 to 12 will not be assigned phenobarbital as one of the intervention ASM and the loading dose of one of the two ASM selected will be omitted. In this case the ASM list doses remain the same, and the recommended intervention will be Levetiracetam with loading and maintenance doses and lacosamide only maintenance doses.
 
For all participants, the protocol driven ASM can be continued, suspended or modified by the care team after the repeat rs-fMRI is obtained. ASM administration after the follow up scan is not considered part of the protocol intervention. Step-wise withdrawal is encouraged in case the care team decides to suspend the ASM given as part of the protocol.

Outcome Measures	
Definitions are provided in the abbreviations table.
 
Aim 1. Pre and Post treatment SzNET activity Aim 1a. Pre and post-treatment SzNET total volume medians Aim 1b. Pre and post-treatment SzNET power spectrum medians
 
Aim 2. Presence of SzNET in rs-fMRI #1 (binary)
 
Aim 3. Follow-up EEG improvement (binary).

	
Aim 4. Connectivity improvement of typical RSN in MSABI patients after intervention (Binary).
 
Aim 5. Follow up outcomes (3 months from hospital discharge) collected from one of the NSICU Post-Discharge Clinics, include: NDDI-E, PROMIS emot. Dist. -Anxiety - Short form, Liverpool Adverse Events Profile questionnaire, QOLIE-10-P and MoCA
 
Aim 6.
 
Aim 6a. Enrollment rate.
 
Aim 6b. Dropout rate.

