All patients with an identified SzNET in rs-fMRI#1 will be included in the intervention group. Within one and six days after the first scan, the care team will decide and start the intervention with two ASM agents from the list. The intervention phase occurs between rs-fMRI#1 and the day of follow-up rs-fMRI#2 and repeated EEG. The intervention is considered complete and the follow-up tests can be done if the patient received the study ASM for at least 72 hours after the loading dose start, and the second scan must be done within 72 hours of the last intervention ASM dose. The treatment protocol can continue up to a maximum of ten days to improve the opportunity to schedule the scan. Thus, the rs-fMRI #2 must be done at a time between 73h and 312h (the fourth and thirteenth days) after the intervention phase starts, and the subject can still be receiving the intervention at that time.

Once the rs-fMRI #2 is obtained, the subject's ASM treatment can be continued or changed for clinical reasons depending entirely on the care team's decision, then it will not be considered part of the study's intervention phase or be related to the research team.

The intervention aims to validate the epileptogenic background of the SzNET by using an ASM that is known to be effective. We expect the intervention will influence the improvement of the SzNET. We hypothesize that the intervention will selectively modulate the networks caused by epileptogenic activity, while having less to no impact on abnormal networks caused by other phenomena.

The length of the intervention is designed to be adequate for pharmacological modulation of epileptogenic activity. The six-day time frame between the minimum and the maximum treatment protocol time facilitates a window for the rs-fMRI schedule that is a realistic schedule time frame in the ICU.

From the different ASM options the key intervention and first option to be considered as intervention will be phenobarbital + levetiracetam. This specific ASM combination will be communicated clearly to the ICU care teams as the first line of the study intervention. However, for clinical reasons the care team will be free to select any combination of two or more study listed ASM regimens. On day two of maintenance dosing, the phenobarbital serum level will be measured if it is one of the selected medications, and a new loading dose will be given to aim for a level of 40mcg/ml.

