5.7. Blinding

The Follow-up EEG will be assessed by an epileptologist blinded to rs-fMRI#2 results. Those results will not be posted in the medical records or commented with personnel outside the clinical rs-fMRI service until the follow up EEG and its comparison results should be collected. This blinding doesn't need to be removed to reassure the patient SOC.

6. Treatment Design: Procedures

Description For this uncontrolled, open-label, interventional trial, the intervention will be assigned to all enrolled patients with SzNET+ by the first rs-fMRI. The intervention and its compliance criteria are defined as receiving treatment for three to ten complete days with at least two of the following ASM regimens, simultaneously:

1. Phenobarbital 20 mg/kg intravenous loading dose
2. Levetiracetam 60mg/kg intravenous loading dose
3. Lacosamide 200 mg intravenous loading dose
4. Valproate 30 mg/kg intravenous loading dose
5. Fosphenyton 20 mg/kg intravenous loading dose

All the maintenance dose regimens will start the next day to loading dose, and dosing will be calculated for weight and age of both medications within the combination group, until the repeat rs-fMRI. As soon as possible, the research team will inform the care team that the patient has been allocated to the intervention branch so they can decide on two ASM regimens from the previous list to start the treatment. On the same day, the research team will confirm by medical charts the two ASM selected and the date and the time of the first loading dose infusions. The intervention phase takes the time between rs-fMRI#1 and follow-up rs-fMRI and EEG. The rs-fMRI#2 must be performed after at least three complete days of treatment and no later than eleven days after the beginning of the intervention phase, but in case of ASM withdrawal, the rs-fMRI#2 must be done no later than 72 hours from the last dose. As outcome measures are based on data collected the day of the second rs-fMRI, after that day, the care team will be free to adjust ASM according to what better fits the patient without compromising the protocol.

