Adherence Monitoring/Evaluations the intervention's ASM timing and dosing will be checked from the medical charts. On day two, the phenobarbital serum level will be measured if it was one of the selected medications, and a new loading dose will be given to aim for a serum level of 40mcg/ml.

Concomitant Therapies There are no prohibited or recommended concomitant therapies. Calcium channel blockers must be used with precaution when administering some of the protocol ASM (see appendix B & E).

Follow-up tests (Days 3-13 from Start of Loading Dose)

- Order Post-Intervention research-related rs-fMRI (#2)
 - Scan must be **performed** after completing a minimum of 72h of intervention ASM protocol (including loading and maintenance doses).
 - Scan must be **completed** within 72hrs of last intervention ASM dose.
 - **To undergo any study indicated rs-fMRI, the participant should not have been diagnosed with vasospasm based on their most recent transcranial Doppler examination, conducted within the last 3 days.**
 - Post scan, the participant can continue on their current ASM regimen or be changed based on routine clinical care decisions.
 - The official results report will be uploaded to EPIC after the post-intervention research-related EEG has been reported.
 - AE Review:
 - Review Dropout data (if applicable)
 - Collect GCS Score
- Obtain Post-Intervention research-related EEG
 - EEG characteristics
 - The EEG is a non-invasive medical test with very low risk of adverse events. Very rare complications could be associated with skin reactions to the conducting material used for the electrodes and malfunction of the device.
 - Bedside monitoring.
 - Minimum 1 hour run.
 - Without Photostimulation.
 - EEG recording must be obtained within 72hrs of last intervention ASM dose.
 - Post the EEG, the participant can continue on their current ASM regimen or be changed based on routine clinical care decisions.
 - EEG will be reviewed by a blinded epileptologist for rs-fMRI (#2) results.
 - For ethical reasons the results will be shared with the care team.

7. Schedule of Activities and Procedures

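### The ASM regimen may change once rs-fMRI#2 is done, while the Aim 3 EEG may follow up to 72 hours later, so a SzNET response can be paired with an EEG on another regimen

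*Combined protocol and SAP*

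**What the plan says.** **Release of the regimen.** Four places tie it to the scan.
- Synopsis, Interventions: ASM may be continued, suspended or modified once the repeat scan is obtained, and "ASM administration after the follow up scan is not considered part of the protocol intervention".
- Section 4.1: once rs-fMRI#2 is obtained, "ASM treatment can be continued or changed for clinical reasons". Section 4.1 later explains that the main outcome measures come from that day's data.
- Section 6, opening description: "As outcome measures are based on data collected the day of the second rs-fMRI, after that day, the care team will be free" (that is, free to change the regimen). Here the release comes after the scan day, and the reason covers outcome measures generally, not only the main ones.
- Section 6, Follow-up tests: "Post scan, the participant can continue on their current ASM regimen or be changed based on routine clinical care decisions".

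The same Follow-up tests list then gives a second release, tied to the other test: "Post the EEG, the participant can continue on their current ASM regimen or be changed based on routine clinical care decisions".

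**Timing of the tests.** For the scan, Section 4.1 says "the second scan must be done within 72 hours of the last intervention ASM dose". For the EEG, Section 6 says "EEG recording must be obtained within 72hrs of last intervention ASM dose". Both windows run from the drug. Neither runs from the other test.

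**Hints of a single occasion.** Section 4.1 describes the intervention phase as running to the day of the follow-up scan and repeated EEG. The variables table in Section 4.3 places EEG improvement at occasion 2, defined as rs-fMRI#2, alongside the volume and power-spectrum measures.

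**Analysis.** Section 8.3 fits a logistic regression of EEG improvement on more than 50% SzNET improvement, in 22 subjects.

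**The concern.** Aim 3 asks whether EEG improvement goes with SzNET response to the study treatment. That needs both measurements to reflect the same exposure. The reason Section 6 gives for releasing the regimen, that outcome data are collected on the scan day, is not secured for the EEG. A stop, swap or escalation between the two tests affects one side of the pair only.

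Two effects are possible. If changes are unrelated to the patient's course, the EEG contrast between SzNET responders and non-responders is blurred. If changes follow the patient's course, for example escalation in a worsening patient, the EEG partly reflects the newer regimen and the association can move either way. With 22 subjects, a few such pairs can alter the estimate.

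**Working it through.** **1. The plan's own timing figure.** Section 4.1 allows up to ten days of treatment and a scan within 72 h of the last dose: 10 × 24 + 72 = 312 h, as stated there. Section 9 gives no power or detectable effect for Aim 3, so there is no such figure to reproduce.

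**2. Scan-to-EEG gap after a release at the scan.** ASM given after the scan is not intervention (Synopsis), so the last intervention dose is at or before the scan. Let *d* be the hours from that dose to the scan. The EEG may then follow the scan by at most 72 − *d* hours. Maintenance is 12-hourly (Section 4.1), so the number of dosing slots in the gap is at most (72 − *d*)/12, rounded down.

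| Last dose before scan (*d*) | Latest EEG after scan | 12-hourly slots |
|---|---|---|
| 0 h | 72 h | 6 |
| 12 h | 60 h | 5 |
| 24 h | 48 h | 4 |
| 48 h | 24 h | 2 |
| 72 h | 0 h | 0 |

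A patient still on 12-hourly dosing at the scan has *d* between 0 and 12 h, so the permitted gap is 60 to 72 h. The minimum intervention is itself 72 h.

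**3. Whether another rule closes the gap.**
- Dropout (Section 7.8) depends on two-drug treatment for at least 72 h and on obtaining rs-fMRI#2 in window. An EEG on a changed regimen does not trigger it.
- The variables table (Section 4.3) lists days of ASM and the times to each scan and to treatment start. It lists neither the time of the EEG nor the regimen at the EEG.
- The Aim 3 model (Section 8.3) has no term for regimen or timing.
- Section 8.1 records protocol departures, but this sequence is not a departure.

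**4. Illustration of dilution.** These rates are assumptions, not figures from the documents: 11 SzNET responders and 11 non-responders; EEG improvement 80% and 30% on the study regimen; 55% in both groups when the EEG is on another regimen. With a fraction *f* of EEGs off-regimen, each group's rate is (1 − *f*) × its own rate + *f* × 0.55. At *f* = 0.25 the responder rate is 0.75 × 0.80 + 0.25 × 0.55 = 0.738, and the non-responder rate is 0.75 × 0.30 + 0.25 × 0.55 = 0.362.

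| *f* | Rates | Relative risk | One-sided z power | One-sided Fisher power |
|---|---|---|---|---|
| 0 | 0.800 vs 0.300 | 2.67 | 0.80 | 0.70 |
| 0.25 | 0.738 vs 0.362 | 2.03 | 0.55 | 0.44 |
| 0.50 | 0.675 vs 0.425 | 1.59 | 0.32 | 0.22 |
| 1 | 0.550 vs 0.550 | 1.00 | 0.05 | 0.03 |

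The table covers only non-selective changes. Changes that depend on the patient's course could bias the result in either direction.

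**The case against.** The strongest reply is that same-day testing is plainly intended. Section 4.1, the opening of Section 6 and the occasion code in Section 4.3 all point that way, and if sites work so, the gap does not arise. This stands as evidence of intent and makes the problem one of inconsistent wording more than a chosen separation of the tests. It does not make a rule: Section 6 and the Table of Events (Section 7.1) give only a day 3 to 13 range for the follow-up tests.

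Second, Section 4.1 speaks only of the main outcome measures. The imaging measures are primary and EEG improvement is secondary, so that sentence is correct as it stands. Only the Section 6 version reaches too far.

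Third, exposure already varies. Additional ASM and swaps between listed drugs are allowed before either test (Sections 6 and 7.8), and the scan itself may come up to 72 h after the last dose. Scan results are also withheld until the EEG is reported (Sections 5.7 and 6), so the scan result should not prompt the change. All this is true, and it limits one route of bias. But a swap before both tests affects both, a change between them affects one, and the clinical course can still prompt it.

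A reader might also infer a gap of about ten days with the EEG first: hour 73 to hour 312 is 239 h. That rests on reading the last dose as the latest dose before the EEG, and on the 312 h limit. The eleven-day limit in the opening of Section 6 gives 11 × 24 − 73 = 191 h. If the EEG must lie within 72 h either side of the final study dose, an EEG at hour 73 puts that dose by hour 145 and the scan by hour 217, a gap of at most 144 h. With the EEG first there may also be no regimen change at all. The point here does not depend on any of these figures.

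**Conclusion.** The concern holds in a limited form. As written, the plan allows a scan on the study drugs, a regimen change, and an in-window Aim 3 EEG up to 72 h after the scan. This 72 h is an upper bound and shrinks hour for hour if dosing stopped before the scan. All 22 planned Aim 3 subjects come under the rule, but the documents give no basis for estimating how many would have a change between the tests. The loss of association and power shown above is therefore illustrative.

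It would be going too far to call the Aim 3 pairing invalid. Dilution, or bias of unknown sign, is what the text supports. Nor do the documents settle which test ends the intervention phase: the Synopsis points to the scan, while Sections 4.1 and 6 also name the EEG. Those statements have to be reconciled by the investigators. The primary imaging outcomes of Aim 1 are not affected by a change made after the scan.

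**What to change.** 1. Reconcile the Synopsis, Section 4.1 and both parts of Section 6 on the order of scan, EEG and ASM release, without restricting the care team's treatment decisions.
2. Schedule the research EEG, already planned as a bedside recording of at least one hour, on the same calendar day as rs-fMRI#2 and, where possible, before any ASM change made after the scan. An open-ended option to do it before the scan would leave long gaps, and EEG results go to the care team.
3. Add to the variables table the date and time of the EEG and, at both tests, the ASM regimen and the hours since the last intervention dose.
4. In Section 8.3, keep all pairs in the main Aim 3 model and pre-specify a sensitivity analysis limited to pairs measured on the same regimen. Dropping off-regimen pairs from the main model would select on a post-treatment event that may itself depend on the patient's course.

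The cost is slightly tighter EEG scheduling, a few data fields, and wording changes in the Synopsis and Sections 4.1, 4.3, 6 and 8.3. No additional test is needed.

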The study's main intervention option consists of the Phenobarbital and Levetiracetam regimens. However, the clinical team can select any combination of two or more ASM regimens from the list provided, for clinical reasons. On day two of intervention, the phenobarbital serum level will be measured if it was one of the selected medications, and a new loading dose will be given to aim for a serum level of 40mcg/ml.

Participants with GCS 9 to 12 will not receive phenobarbital as one of the intervention anti-seizure medications (ASM), and the loading dose of one of the two selected ASMs will be omitted. For these participants the study's main intervention option consists of the Levetiracetam and Lacosamide regimens, omitting the Lacosamide loading dose.

Rs-fMRI schedule (Day 0-1 of Enrollment)

- Order Pre-Intervention research-related rs-fMRI#1

Time from enrollment to intervention start (Days 1-6 of Enrollment)

- Scan **should** be performed within 3 days **from enrollment**.
- **To undergo any study indicated rs-fMRI, the participant should not have been diagnosed with vasospasm based on their most recent transcranial Doppler examination, conducted within the last 3 days.**
- The time frame between fMRI scan and intervention start will range from 1 to 6 days.
- Obtain (research driven) fMRI
 - What is rs-fMRI
 - ♦ MRI generates images based on the interaction of the body with potent electromagnetic fields.
 - ♦ Rs-fMRI uses BOLD signal to identify vascular reflexes related to neuronal activation.

- What is the process of transporting the patient to the fMRI?
 - ◆ As SOC at UNC Health, a transport team made of two nurses, one fellow physician and one respiratory therapist gathers with the patients at ICU and checks to have the required equipment for transportation.
 - ◆ The subject is transported by the transport team from the ICU to the MRI Scan within the hospital, located on the first floor or the basement of the same ICU building, according to the MRI scanner availability.
 - ◆ Once the rs-fMRI scanning is acquired the transport team transports the subject back to the ICU.
- How long does the fMRI routinely last?
 - ◆ Around 25 minutes for the scanning
 - ◆ Variable transportation times, from ICU to scanner and from scanner to ICU
- What are the risks associated with the fMRI?
 - ◆ Patients meeting eligibility criteria do not have risk of adverse events related to the electromagnetic fields

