 - ◆ Rs-fMRI does not require contrast agents to be administered.
 - ◆ In case of tattoos with suspected high levels of ferromagnetic compounds cold compresses can be applied to prevent heating.
 - ◆ Transportation through the hospital to perform the MRI scan can be associated with mechanical risks and support devices malfunction. Trained personnel is in charge of the process, which is supervised by a physician.

○ SzNET Stratification of rs-fMRI

- SzNET (-): with EEG (+) or EEG (-).
 - ◆ N=32
 - ◆ No protocol Intervention-driven, combined ASM is administered.
 - ◆ They will not receive the second fMRI.
 - ◆ They will only be followed at the 3 months post discharge visit if they are scheduled to one of the NSICU Post-Discharge clinics.
 - ◆ MRI scan transportation related AE Review.
- SzNET(+): with EEG(+).
 - ◆ N=11
 - ◆ Proceed with combined ASM Intervention.
 - ◆ Intervention **must** start within 1 to 6 days after enrollment.
 - ◆ AE Review.
- SzNET(+):with EEG(-)
 - ◆ N=11
 - ◆ Proceed with combined ASM Intervention.
 - ◆ Intervention **must** start within 1 to 6 days after enrollment.
 - ◆ AE Review.

○ Study team will inform the family of the rs-fMRI results and upload the official report to EPIC.

Intervention start (Days 1-6 from Enrollment)

- **Clinical Care Team** will choose the intervention regimen.
 - If participant was already on **two** of the protocol-approved ASM, the participant will be required to start the intervention by administering the protocol-driven loading dose infusions outlined for

each of the combined ASMs, or by administering the loading dose for any of the other 5 listed ASM options. A third option in this case is to administer protocol-driven loading dose of one of the current medications and add another of the 5 ASM loading dose and maintenance regimen.

- If participant was already on **one** of the protocol-approved ASM, the participant will be required to start the intervention by administering the protocol-driven loading dose outlined for the ASM that the participant was previously receiving *along with* another protocol-driven ASM loading dose from the ones listed on the protocol.
- If participant **was not receiving any** of the protocol approved ASM, the participant will be administered a loading dose of two of the 5 protocol approved ASM.
- If the clinical care team does not want to use a combination of two of the 5 protocol-approved ASMs, they will not be enrolled into the study.

- **Research Team** will

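### Section 6 requires a participant already on one listed antiseizure drug to be re-loaded with it, which disagrees with the synopsis, Section 4.1, Section 6's own general rule and the GCS 9 to 12 rule

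*Combined protocol and SAP*

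**What the plan says.** Four places govern which drugs start the intervention.

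- **Synopsis, Interventions.** It sets a default: "Participants that are SzNET positive will receive a loading ASM combination dose of Levetiracetam (60mg/kg) and Phenobarbital (20 mg/kg"). Both drugs are then continued at maintenance doses. It also gives a condition for departing from this default: "If care team considers either of those medications cannot be used, then they are allowed to administer any other combination of two ASM" on the list.
- **Section 4.1.** Phenobarbital plus levetiracetam is the first option, but "for clinical reasons the care team will be free to select any combination of two or more study listed ASM regimens".
- **Section 6, opening description.** It has the same main option, and "the clinical team can select any combination of two or more ASM regimens from the list provided, for clinical reasons".
- **Section 6, Intervention start.** After giving the choice of regimen to the care team, it sets rules by prior ASM use. With one listed ASM on board, the first step is mandatory: "administering the protocol-driven loading dose outlined for the ASM that the participant was previously receiving". A loading dose of a second listed ASM is required as well. With two on board, there are three routes: re-load both, re-load one and add another, "or by administering the loading dose for any of the other 5 listed ASM options".

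The synopsis, Section 4.1 and the opening of Section 6 add that participants with GCS 9 to 12 do not get phenobarbital as an intervention drug and that one of the two loading doses is left out. The main option in Section 6 for this subgroup is levetiracetam with a load and lacosamide without one.

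If phenobarbital is used, its serum level is measured on day two and, in the words of Section 4.1, "a new loading dose will be given to aim for a level of 40mcg/ml".

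**The concern.** The re-load rule is worded as a requirement. The other three places carry no exception for drugs already on board, and nothing says which text prevails. Staff reading different pages could therefore start different regimens in the same patient.

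Prior ASM use is foreseeable here. Section 4 has patients on standard care, including antiseizure therapy, before the first scan, and Sections 2.1 and 4.1 describe empirical ASM use as common in this population. What changes between the two scans also depends on the reading: two new drugs, or one new drug plus a re-load of an existing one. Aim 1 in Section 8.3 analyses all treated participants together in an intercept-only model, and the variable table in Section 4.3 lists no baseline item for prior ASM.

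**Working it through.** The plan states no figure on this point, so the check is a comparison of texts plus a count of drug pairs.

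**Step 1. A SzNET+ participant with GCS below 9, already on valproate alone.**

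| Place | Regimen for this participant | First-line pair as a two-drug regimen? |
|---|---|---|
| Synopsis | Levetiracetam + phenobarbital, unless one is considered unusable | Yes, the default |
| Section 4.1 | That pair first; any combination of two or more for clinical reasons | Yes |
| Section 6, opening | The same | Yes |
| Section 6, Intervention start | Valproate re-load + one other listed drug | No |

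**Step 2. Count the pairs.**

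- Five listed drugs give 5 × 4 / 2 = 10 two-drug pairs.
- Pairs that contain a given current drug: 5 − 1 = 4. The re-load rule therefore removes 10 − 4 = 6 of the pairs that Section 4.1 permits.
- Phenobarbital + levetiracetam is among the 4 if the current drug is phenobarbital or levetiracetam. It is not among them for lacosamide, valproate or fosphenytoin (3 of the 5 drugs).

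**Step 3. The same count for GCS 9 to 12.**

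- Without phenobarbital, four drugs give 4 × 3 / 2 = 6 pairs.
- A participant on one of those four drugs keeps 4 − 1 = 3 of them. The subgroup's main pair, levetiracetam + lacosamide, survives if the current drug is either of those two, but not if it is valproate or fosphenytoin.
- A participant on phenobarbital keeps 0: the required re-load is a drug that the subgroup may not receive as part of the intervention.
- Whatever the current drug, the re-load rule calls for two loading doses, while the subgroup rule omits one. A participant on lacosamide shows the clash directly: one text requires a lacosamide load, and the subgroup's main option leaves it out.

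**Step 4. The list against itself.** A participant on two listed drugs may move to other listed drugs, but a participant on one has no such route. The text for those on two refers to five other options, when 5 − 2 = 3 remain.

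**Step 5. Phenobarbital already on board.** The re-load rule applies the listed load without mentioning an existing serum level. The 40 mcg/ml level in Sections 4.1 and 6 comes in only with the day-two measurement. The documents do not say how the two relate.

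**The case against.** The strongest defence is that the re-load text is a specific start-up rule inside a general freedom of choice: its own list begins by leaving the regimen to the care team. That reading is possible, but no passage states an order of precedence. The wider options for participants already on two drugs also sit badly with it, although that asymmetry alone is not a contradiction. Nor does it meet the synopsis, which is stricter than Section 4.1, or the GCS 9 to 12 rule.

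Some stronger readings are tempting but not supported:

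- **That the synopsis also leaves the combination to the care team.** It sets a default pair and a condition for leaving it. It disagrees with the re-load rule from the stricter side.
- **That everyone on a third drug loses the first-line pair.** Participants with GCS 9 to 12 are barred from phenobarbital in any case. For the others, Sections 4.1 and 6 allow two or more drugs, and Section 6 allows additional ASM, so a three-drug regimen could contain the pair.
- **That re-loading phenobarbital breaches the protocol's own target.** This needs a distribution volume and a starting level, neither of which is in the documents. It also treats 40 mcg/ml as a ceiling, whereas the text gives a level to aim for when adjusting.
- **That the affected participants are mostly EEG+.** No passage says so, and Section 2.1 links empirical ASM use to cases where the EEG is inconclusive.
- **That Aim 1 is invalid because regimens are pooled.** Section 4 deliberately permits alternative regimens in this pilot. Reconciling the rules would not make the intervention uniform.

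**Conclusion.** The inconsistency is in the current text and stands. For GCS below 9 with lacosamide, valproate or fosphenytoin as the only listed ASM, the re-load rule leaves 4 of 10 pairs and excludes the first-line pair as a two-drug regimen, against three other places that offer it. For GCS 9 to 12 the contradiction is sharper: two loads against one, and no compliant regimen if the current drug is phenobarbital. The missing switch option for participants on one drug, the miscounted remaining drugs and the unstated link to the phenobarbital level are lesser gaps in the same list.

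The result rests on the wording and on counting pairs from the five listed drugs, with no outside figure. How many of the 22 participants expected to be treated (Section 5.1) enter on exactly one listed ASM is not given, so the effect on the Aim 1 estimate cannot be sized. This is worth correcting because it is a stated treatment rule and cheap to repair. It is not a flaw in the primary analysis.

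**What to change.** Reconcile the Intervention start list in Section 6 with the synopsis, Section 4.1 and the opening of Section 6, so that one rule governs participants already on one or two listed ASMs. The reconciled text should cover three things: how the rule applies at GCS 9 to 12, how re-loading phenobarbital already on board relates to the level aimed for on day two, and which drugs remain for a participant already on two. The clinical rule is for the sponsor. The cost is a wording amendment.

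Optionally, record which listed ASMs are in use at rs-fMRI #1 and describe the Aim 1 changes by prior listed ASM use. Staff must already know this to apply the list, and Section 10.2 already provides for entering concomitant medications, so the added data work is small. The drawback is small cells: Section 5.1 plans for 20 participants with both treatment and a repeat scan, so a split by none, one or two prior drugs would be descriptive only.
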